6.5.6 Treatment Guidelines for Other Non-Hematologic Toxicity

The table below provides treatment guidelines for treating tarloxitinib non-hematologic toxicities other than QT prolongation and infusion-related reactions.

Toxicity (CTCAE v5.0)	Details	Hold Dose	Dose Levels After Recovery to \leq Grade 2 or Baseline
Grade 2	Intolerable skin toxicity or diarrhea	Hold dose until resolution to Grade 0 or 1 or Grade 2 tolerable	If symptoms are intolerable, recurrent, or not controlled by supportive care, hold dose until symptoms improve and reduce to next lower dose level
Grade 2	ALT or AST $> 3 \times$ ULN	Hold dose until resolution to $<$ Grade 2 or baseline	150 mg/m ² (no reduction)
	ALT or AST $> 3 \times$ ULN (Grade 2) AND a total bilirubin $\geq 2 \times$ ULN (patients without liver metastasis)**	Treatment to be discontinued	Not applicable
Grade 3	Nausea and vomiting*	Hold dose until resolution to Grade 0 or 1 or Grade 2 tolerable	120 mg/m ² ; if recurs, then second reduction to 75 mg/m ²
Grade 4	Pulmonary embolism that is adequately treated	Hold dose until resolution to Grade 0 or 1	120 mg/m ² ; if recurs, then second reduction to 75 mg/m ²
Grade 4	All other life-threatening conditions	Treatment to be discontinued	Not applicable

ALT = alanine aminotransferase; ASP = aspartate aminotransferase; CTCAE = Common Terminology Criteria for Adverse Events; ULN = upper limit of normal

* May hold or reduce if nausea/vomiting continues despite optimized anti-emetic treatment

** Tarloxitinib-related toxicity meeting the definition of Hy's Law, tarloxitinib will be discontinued permanently

6.5.7 Compliance

Investigators are required to conduct the study in compliance with the protocol. Compliance with the protocol will be closely monitored. Important aspects of compliance with this clinical trial include:

- Eligibility,
- Tarloxitinib administration, including:
 - Dose calculation
 - Dose modification
 - Infusion duration
- Performance of protocol-specified assessments,
- ECG monitoring, and
- AE monitoring.

Protocol deviations are defined as any departure from the protocol or associated instructions and will be monitored. Deviations from the protocol, including violations of inclusion/exclusion criteria, will be assessed as “minor” or “major.” Protocol deviations at investigational sites will be discussed with the Investigator and additional training will be provided as needed to secure Investigator compliance.

Study staff will receive additional training as needed to prevent non-compliance.

7 DRUG INFORMATION

Tarloxitinib will be administered intravenously once weekly. Sotorasib will be self-administered orally by subjects daily.

7.1 TARLOXOTINIB

7.1.1 Tarloxitinib Administration

Tarloxitinib will be administered as an IV infusion using an IV infusion or syringe pump and a 0.2-micron inline filter. Tarloxitinib may be infused with latex-free polyvinyl chloride or polyolefin containers and equipment.

7.1.2 Tarloxitinib Dose Calculation

All patients will receive a weekly tarloxitinib infusion at the RP2Dc determined in the safety lead-in portion of the trial. administered as a 1-hour IV infusion on Days 1, 8, 15, and 22 of each 28-day cycle until disease progression or unacceptable toxicity. The dose administered will be based on the patient’s body surface area (BSA) determined on Day 1 of each cycle or within 7 days (e.g., Day 21 of the prior cycle). The DuBois and DuBois formula for BSA calculation is:

BSA = (W 0.425 x H 0.725) x 0.007184

Investigational sites are instructed to use the DuBois and DuBois formula but may also use the

formula/method in current institutional practice if accurate dose calculation can be assured.

Tarloxotinib doses within a cycle do not need to be adjusted unless there is a > 10% change in weight.

7.1.3 Tarloxotinib Infusion Duration

Tarloxotinib infusions must be at least 1 hour (60 minutes) in duration. The tarloxotinib infusion can be slowed or interrupted in the event of infusion-related reactions. If the tarloxotinib infusion is interrupted, it should be restarted at one-half the infusion rate after the symptoms of the infusion-related reaction have resolved.

7.1.4. Tarloxotinib Administration Schedule

Tarloxotinib will be administered on Day 1, Day 8, Day 15, and Day 22 of every 28-day cycle.

All infusions after Cycle 1 Day 1 will be administered 7 days \pm 1 day after the prior infusion.

Investigators are instructed to avoid dose schedule modifications whenever possible, especially within the first 3 cycles of study treatment. The reason for the dose schedule modification should be recorded in the eCRF.

7.1.5 Dose Delays

All dose schedule modifications of > 1 day must be discussed with the Principal Investigator (or designee). Intentional cycle delays of > 1 day (e.g., patient vacation, physician requested “drug holiday”) must be approved by the Principal Investigator (or designee). Study visits will align with tarloxotinib infusion days. If a tarloxotinib dose must be delayed > 3 days, this will be considered a missed dose.

7.1.6 Missed Doses

If a patient misses a dose due to hospitalization or any other reason, the next dose received will be referred to as the next scheduled dose (e.g., If a patient misses their Cycle 1 Day 22 infusion, the next dose will be administered at their Cycle 2 Day 1 visit.). If a patient must miss their Cycle 2 Day 1 dose, the assessments that were planned for this visit (e.g. ECGs) should be collected at the Cycle 2 Day 8 visit to ensure adequate data is collected for these endpoints. For other missed visits, any assessments that were part of the missed visit, but are not part of the next visit (i.e., no need to duplicate tests) should be collected, if possible, at the next visit.

Radiographic tumor assessments should continue per the Study Schedule (i.e., every 8 weeks [\pm 5 days] from Cycle 1 Day 1) regardless of changes to the dosing schedule.

If there is an unavoidable delay of an infusion due to COVID-19, the Principal Investigator should be informed as soon as possible. The infusion should be rescheduled based on Investigator judgment, taking into consideration the patient’s safety.

7.1.7 Supportive Care

All patients may receive steroid or anti-emetics premedication prior to tarloxotinib infusions. The premedication regimen will be determined by the Investigator and may be adjusted at subsequent infusions based on the signs and symptoms observed during or after prior infusions.

Additionally, patients may be discharged with take-home prophylactic medications.

The tarloxotinib Phase 1 and 2 studies demonstrated that tarloxotinib is associated with non-hematologic toxicities. These included mainly low-grade skin rash and diarrhea typical of that observed with EGFR TKIs. For this reason, prophylaxis and treatment for these toxicities should be considered following institutional guidelines, similar to another EGFR TKI such as erlotinib or afatinib.

Infusion-related reactions were observed in patients receiving tarloxotinib. These reactions were characterized by flushing, urticarial skin rash, pruritus, and hypotension occurring during or immediately following the infusion of tarloxotinib. Patients who experienced an infusion reaction with the first dose of tarloxotinib received prophylactic steroids prior to subsequent doses, which reduced the severity of infusion reactions. Therefore, prophylaxis for drug hypersensitivity reactions that may include a glucocorticoid and an anti-histamine may be considered prior to each tarloxotinib dose according to institutional guidelines.

Nausea and vomiting have occurred in patients in the Phase 1 and 2 studies; therefore, anti-emetic prophylaxis for minimally to moderately emetogenic regimens should be considered after Cycle 1 Day 1 according to institutional guidelines. Prophylaxis against nausea and vomiting in the tarloxotinib studies was based on metoclopramide as a single agent. If a 5-HT3 antagonist is required, palonosetron should be employed, if possible, as it is considered to have the least potential among 5-HT3 antagonists for QT prolongation.

7.1.8 Potassium Supplementation

Serum electrolytes (including potassium) will be checked prior to each tarloxotinib infusion.

- Tarloxotinib will not be administered if the serum potassium level is < 3.5 mEq/L.
- Patients with a serum potassium of < 3.5 mEq/L will receive potassium replacement per institutional policy (IV and/or oral) and have the scheduled tarloxotinib infusion delayed at least 24 hours and potassium levels rechecked within 1 hour prior to the rescheduled infusion.

All patients who present with a serum potassium level of ≥ 3.5 mEq/L will be given potassium supplementation prior to tarloxotinib infusion based on pre-infusion serum potassium result:

Potassium Supplementation Guidelines Pre-infusion	
Serum Potassium (mEq/L)	Potassium Supplementation Strategy
< 3.5	
• Hold tarloxitinib• Administer potassium replacement per institutional policy (IV and/or PO)• Delay the scheduled tarloxitinib infusion delayed at least 24 hours and potassium levels rechecked within 1 hour prior to the rescheduled infusion
3.5 to 4.0	
• All patients will be supplemented daily with 20 mEq of potassium (IV or PO).
> 4.0	
• Administer potassium replacement per institutional policy (IV and/or PO)

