6.5 TREATMENT AND RETREATMENT CRITERIA

The results of tumor assessments are not required for the initiation of subsequent cycles, but patients must meet the following criteria before receiving each tarloxotinib infusion. **Note:** all ECG dose modifications will be based on the average manually measured QTcF.

- No QTcF of \geq 601 msec during any previous infusion

Note: Patients with QTcF of \geq 501 msec and $<$ 601 msec during or following the prior infusion MUST be dose reduced. If QTcF prolongation is \geq Grade 3, an ECG may need to be repeated more frequently during a patient's visit as clinically indicated, depending on the degree of the prolongation and per institutional standards.

- Check serum electrolytes
 - Pre-infusion magnesium and calcium in normal range, unless an exception is approved by the Principal Investigator.
 - If other electrolytes (e.g., sodium, chloride) are outside of the normal range, patient can receive tarloxotinib infusion if it is deemed safe per Investigator discretion.
 - Pre-infusion serum potassium must be \geq 3.5 mEq/L.
- Pre-infusion ECG: No evidence of second- or third-degree atrioventricular block
 - QTcF interval of $<$ 450 msec
- Skin rash of \leq Grade 2
- Gastrointestinal toxicity of \leq Grade 2
- Any other clinically significant tarloxotinib-related toxicity must return to at least Grade 2.

All patients not meeting retreatment criteria must be discussed with the Principal Investigator and possible dose/schedule modification and/or study treatment discontinuation discussed.

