*** Every 8 weeks (+/- 5 days) from Cycle 1 Day 1***

Every visit

Every visit

CT = Computed tomography, ECOG = Eastern Cooperative Oncology Group, EOI = End of Infusion, EOT = End of Treatment, SFU = Safety Follow-up, MRI = Magnetic Resonance Imaging, PET= Positron Emissions Tomography, QTcF = Corrected QT interval as calculated according to Fridericia's formula, SCR = Screening period

¹ For patients with Grade 3 QTcF prolongation (≥ 501 msec or > 60 msec increase compared to pre-infusion), repeat ECG every 15 to 30 mins until resolved to Grade 2 (481 to 500 msec) or lower (≤ 480 msec) and then obtain ECGs every hour up to 4 hours post infusion, or longer as clinically indicated.

² Serum pregnancy test at baseline, then urine pregnancy test, for women of childbearing potential

³ Collect blood for biomarkers per correlates manual.

⁴ If required. See section 7, potassium supplementation.

⁵ Perform radiographic assessments according to institutional practice. Include CT or MRI of the chest and abdomen, and if applicable, brain CT or MRI, bone scan, or PET-CT at screening. The baseline tumor assessment is required within 28 days prior to first dose of tarloxotinib. PET-CT may be substituted for a contrasted CT of the chest and abdomen if tumor measurements are obtained per RECIST 1.1 criteria. The same imaging modality used for baseline imaging must be used for subsequent tumor assessments in each patient.

⁶The EOT visit should be conducted within +/- 7 days of the last dose of tarloxotinib, and the safety follow-up should occur 30 days (+/- 7 days after the last dose of tarloxotinib).

⁷Patients may be followed for survival status every 3 months for up to 6 months after the last patient on study visit (LPV) at the investigator's discretion.

⁸Informed consent, medical history and physical exam/ECOG status to be obtained within 28 days of Cycle 1 Day 1. Baseline labs and ECG are to be obtained within 14 days of Cycle 1 Day 1.

⁹ Vital signs should include: Height (at screening only), weight, blood pressure, temperature, respirations, and O₂ saturation.

¹⁰ Liver function testing to be performed every 3 weeks for the first 3 months, then monthly as clinically indicated.

Cycles are 28 days in length. Study visits have a +/- 1 day window to allow for holidays or other rescheduling reasons, to be documented in the research record.

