11.1.2 POPULATIONS FOR ANALYSES

The following analysis sets will be defined for this study.

The **safety analysis set** comprises all enrolled patients who receive any quantity of study treatment, regardless of eligibility. The safety evaluation will be performed based on the first dose of study treatment a patient receives, regardless of the patient's cohort assignment. The safety analysis set will be used for all dosing/exposure and safety analyses.

The **DLT-evaluable population (safety lead-in only)** comprises patients who have either completed the DLT-observation period (1 cycle, 28 days) and received at least 75% of planned doses of the tarloxotinib and sotorasib combination in cycle 1 or have discontinued study treatment or study participation before completing cycle 1 due to a DLT.

The **intention to treat (ITT) analysis set** comprises all patients in the safety analysis set eligible for study inclusion and who meet the inclusion criteria for dose expansion, including eligible safety lead-in patients treated at the RP2D_c. This analysis set will be used for all efficacy analyses.

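### Section 7.1.8 calls for potassium before every tarloxotinib infusion at 3.5 mEq/L or above, and states no upper level at which it is withheld (low severity)

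*Combined protocol and SAP*

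**What the plan says.** Section 7.1.8 has serum electrolytes, including potassium, checked before each tarloxotinib infusion. Below 3.5 mEq/L, tarloxotinib is held, potassium is replaced, the infusion is put back by at least 24 hours and the level is rechecked. For everyone else, the section says that patients "with a serum potassium level of ≥ 3.5 mEq/L will be given potassium supplementation prior to tarloxotinib infusion based on pre-infusion serum potassium result", and a table with three rows follows.

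- **Below 3.5 mEq/L:** hold and delay as above, with the line "Administer potassium replacement per institutional policy (IV and/or PO").
- **3.5 to 4.0 mEq/L:** a fixed amount, "All patients will be supplemented daily with 20 mEq of potassium (IV or PO").
- **Above 4.0 mEq/L:** no upper end, and one instruction only, which repeats the replacement line of the first row word for word.

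Two other places bear on the rule. Section 6.5 (retreatment criteria) gives potassium its own line, "Pre-infusion serum potassium must be" at least 3.5 mEq/L, again with no upper bound. In the study calendar (section 9.2), supplementation is marked at the infusion visits with footnote 4: "If required. See section 7, potassium supplementation".

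**The concern.** The result that would show a high potassium is in hand before every infusion, but the protocol does not say at what level potassium should stop being given. The general sentence in 7.1.8 covers everyone at or above the floor, and the row that a high result falls into begins with an instruction to administer. The row also reads oddly: a patient whose level is comfortably adequate gets the same replacement line as one too low to be infused, while the patient in between gets a fixed amount. The documents do not show whether the repetition was intended or is a copying slip.

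What is at stake is patient safety and clarity of instruction. Giving potassium to a patient who is already above normal is an avoidable risk, and a protocol should not rely on staff departing from its wording to avoid it.

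**Working it through.** No arithmetic applies, and the plan has no figure to reproduce. The check takes a patient whose pre-infusion potassium is above the site's ULN and reads each relevant text in turn. The documents give no ULN for potassium. I assume only that it lies above 4.0 mEq/L, so that such a patient falls in the last row.

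| Text | What it does with a value above the ULN | Withholds potassium? |
|---|---|---|
| 6.5, potassium line | Met, because only a minimum of 3.5 mEq/L is set | No |
| 6.5, other electrolytes | At most, leaves the infusion to the Investigator | No |
| 7.1.8, general sentence | Included, because it covers all values from 3.5 mEq/L upward | No |
| 7.1.8, last table row | Included; replacement according to local policy, no amount stated | Not in the protocol; local policy might |
| 9.2, footnote 4 | Conditional, then refers back to section 7 | Not stated |

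1. **The general sentence.** It has a lower bound and no upper bound. This does not depend on how the table came through PDF extraction, because the gap is in the prose as well.
2. **The table.** One of its three rows is open-ended upward, and none of the three says to give no potassium.
3. **Section 6.5.** Magnesium and calcium must be in the normal range unless the Principal Investigator approves an exception, which is a two-sided limit. Potassium gets a floor only. The next provision says that if "other electrolytes (e.g., sodium, chloride) are outside of the normal range, patient can receive tarloxotinib infusion if it is deemed safe per Investigator discretion". Whether a high potassium counts as one of these is arguable, since potassium has a line of its own. Either way, that provision decides whether to infuse, not whether to give the supplement.
4. **Footnote 4.** Its condition sits uneasily with the general sentence in 7.1.8, and it sends the reader back to that section without naming a level.

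No text that mentions serum potassium states a level at which supplementation stops. The instruction as written therefore extends above the normal range. With infusions on Days 1, 8, 15 and 22, it can apply up to four times in each 28-day cycle.

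**The case against.** The strongest reply is that nobody is told to give a set amount of potassium to a patient with a high value. The general sentence makes supplementation depend on the result and hands over to a table headed as guidelines. The only fixed amount, 20 mEq, is confined to 3.5 to 4.0 mEq/L. Above 4.0 the row refers to institutional policy, which may call for nothing when nothing needs replacing, and footnote 4 is conditional.

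Other safeguards exist. Creatinine clearance must exceed 60 mL/min at screening. ECGs are scheduled before and after infusions. New Grade 3 or 4 laboratory values are recorded as adverse events under section 13.2. Recruitment is from one centre's clinics (5.1), with sub-sites only a possibility (5.1.3), so local policy may vary little.

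Most of this stands, and it is why the risk is low. A reader might infer that the protocol mandates potassium dosing in hyperkalaemia. The documents do not support that: above 4.0 mEq/L they set no dose and leave the matter to local policy. What survives is narrower. The general sentence and the verb in the last row point toward giving potassium, the protocol states no level at which to stop, and the safeguards either monitor the patient or govern the infusion without limiting the supplement.

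**Conclusion.** The point holds as a low-severity clarification. Section 7.1.8, read literally, extends potassium supplementation to patients above the normal range, and neither 6.5 nor the study calendar supplies a ceiling. Confidence is high on the wording and modest on the consequence. Harm would need a high result, a local policy that replaces potassium regardless, and an Investigator who acts on neither the value nor the condition in footnote 4. The documents do not show that any such policy exists. They give no frequency of high pre-infusion potassium, so no event rate can be calculated.

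Some stronger readings should be resisted. A reader might take the limited schedule of post-infusion potassium samples as making the defect larger. It does not, because the instruction acts on the pre-infusion result, which is obtained every time. A reader might also infer a threat to the dose-limiting-toxicity evaluation. Nothing here supports that, and no sample size, power or error rate depends on the point. Whether the 20 mEq is meant every day or only at infusion visits is a separate wording query and adds no weight.

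**What to change.** Amend 7.1.8 as follows.

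- Limit the general sentence to patients from 3.5 mEq/L up to the institutional ULN.
- Change the last row to cover values above 4.0 mEq/L up to the ULN: supplement only if institutional policy calls for it.
- Add a row for values above the ULN: give no potassium; the Investigator reviews the result before the infusion.
- Align footnote 4 of the study calendar with the revised table.

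The floor of 3.5 mEq/L and the 3.5 to 4.0 row stay as they are. Investigator review is preferable to a new mandatory hold in 6.5, because it addresses the supplement without adding a bar to treatment.

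The cost is a wording amendment and a site memo. No new test is needed. Review of a high value may occasionally delay an infusion briefly.

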7.2 SOTORASIB

7.2.1 Description

Sotorasib is an inhibitor of the RAS GTPase family. The molecular formula is C₃₀H₃₀F₂N₆O₃, and the molecular weight is 560.6 g/mol. The chemical name of sotorasib is 6-fluoro-7-(2-fluoro-6-hydroxyphenyl)-(1M)-1-[4-methyl-2-(propan-2-yl)pyridin-3-yl]-4-[(2S)-2-methyl-4-(prop-2-enoyl)piperazin-1-yl]pyrido[2,3-d]pyrimidin-2(1H)-one.

Sotorasib has pKa values of 8.06 and 4.56. The solubility of sotorasib in the aqueous media decreases over the range pH 1.2 to 6.8 from 1.3 mg/mL to 0.03 mg/mL.

Sotorasib is supplied as film-coated tablets for oral use containing 120 mg. Inactive ingredients in the tablet core are microcrystalline cellulose, lactose monohydrate, croscarmellose sodium,

and magnesium stearate. The film coating material consists of polyvinyl alcohol, titanium dioxide, polyethylene glycol, talc, and iron oxide yellow.

7.2.2 Mechanism of Action

Sotorasib is an inhibitor of KRASG12C, a tumor-restricted, mutant-oncogenic form of the RAS GTPase, KRAS. Sotorasib forms an irreversible, covalent bond with the unique cysteine of KRASG12C, locking the protein in an inactive state that prevents downstream signaling without affecting wild-type KRAS. Sotorasib blocked KRAS signaling, inhibited cell growth, and promoted apoptosis only in *KRAS G12C* tumor cell lines. Sotorasib inhibited KRASG12C *in vitro* and *in vivo* with minimal detectable off-target activity. In mouse tumor xenograft models, sotorasib-treatment led to tumor regressions and prolonged survival, and was associated with anti-tumor immunity in *KRAS G12C* models.

7.2.3 Toxicology

Carcinogenicity studies have not been performed with sotorasib.

Sotorasib was not mutagenic in an *in vitro* bacterial reverse mutation (Ames) assay and was not genotoxic in the *in vivo* rat micronucleus and comet assays.

Fertility/early embryonic development studies were not conducted with sotorasib. There were no adverse effects on female or male reproductive organs in general toxicology studies conducted in dogs and rats.

